4.2 Recruitment Plan

A reasonable estimate for accrual of patients for this study is 10-15 patients per month. The anticipated time for completion of this trial is about 2-3 years. Detailed informed consent in plain language will be given to patients for review in either the inpatient or outpatient setting and sufficient time will be given to answer all the questions related to the study. After consent has been signed, pretreatment evaluations will be completed and as outlined in Table 1, Schedule of Assessments, patients will start treatment.

5.0 CRITERIA FOR PATIENT ELIGIBILITY

5.1 Inclusion Criteria

Each subject must meet all of the following inclusion criteria to be eligible to participate in this study:

- Subject must voluntarily sign and understand written informed consent.
- Subject is ≥ 65 years at the time of signing the consent form.
- Subject has histologically confirmed multiple myeloma that has never before been treated (see Appendix II).
- Subject has no prior anti-myeloma treatment therapy within 14 days prior to initiation of study treatment except for corticosteroids with a maximum allowed dosage equivalent to three pulses of dexamethasone (40mg daily for 4 days equals one pulse). Patients may have received prior adjuvant antiresorptive therapy (i.e., pamidronate or zoledronic acid) as routine care, or radiation therapy as palliation for pain and/or spinal cord compression.
- Subject has measurable disease as defined by > 0.5 g/dL serum monoclonal protein, > 10 mg/dL involved serum free light chain (either kappa or lambda) provided that the serum free light chain ratio is abnormal, > 0.2 g/24 hrs urinary M-protein excretion, and/or measurable plasmacytoma(s) of at least 1cm in greatest dimension as measured by either CT scanning or MRI.
- Subject has a Karnofsky performance status $\geq 60\%$ ($> 50\%$ if due to bony involvement of myeloma (see Appendix IV).
- Subject is able to take prophylactic anticoagulation as detailed in section 9.1 (patients intolerant to aspirin may use warfarin or low molecular weight heparin).
- Subject is registered into the mandatory RevAssist® program, and is willing and able to comply with the requirements of RevAssist® program.
- If subject is a female of childbearing potential (FCBP),† she must have a negative serum or urine pregnancy test with a sensitivity of at least 25 mIU/mL within 10 – 14 days prior to and again within 24 hours of prescribing lenalidomide (prescriptions must be filled within 7 days) and must either commit to continued abstinence from heterosexual intercourse or begin TWO acceptable methods of birth control, one highly effective method and one additional effective method AT THE SAME TIME, at least 28 days before she starts taking lenalidomide. FCBP must also agree to ongoing pregnancy testing. Men must agree to use a latex condom during sexual contact with females of child bearing potential even if they have had a successful vasectomy. See

† A female of childbearing potential is a sexually mature woman who: 1) has not undergone a hysterectomy or bilateral oophorectomy; or 2) has not been naturally postmenopausal for at least 24 consecutive months (i.e., has had menses at any time in the preceding 24 consecutive months).

Appendix III: Risks of Fetal Exposure, Pregnancy Testing Guidelines and Acceptable Birth Control Methods.

- Subject has a life expectancy \geq 3 months
- Subjects must meet the following laboratory parameters:
 - Absolute neutrophil count (ANC) \geq 1000 cells/mm³ ($1.0 \times 10^9/L$)
 - Hemoglobin \geq 7 g/dL
 - Platelet count \geq 50,000/mm³ ($50 \times 10^9/L$)
 - Serum SGOT/AST $<$ 3.0 x upper limits of normal (ULN)
 - Serum SGPT/ALT $<$ 3.0 x upper limits of normal (ULN)
 - Serum total bilirubin $<$ 2.0 mg/dL (34 μ mol/L)
 - Creatinine clearance \geq 45 cc/min

5.2 Exclusion Criteria

Subjects meeting any of the following exclusion criteria are not eligible to participate in this study:

- Subject has immeasurable MM (no measurable monoclonal protein, free light chains in blood or urine, or measurable plasmacytoma on radiologic scanning).
- Subject has a prior history of other malignancies unless disease free for \geq 5 years, except for basal cell or squamous cell carcinoma of the skin, carcinoma in situ of the cervix or breast, or localized prostate cancer with Gleason score $<$ 7 with stable prostate specific antigen (PSA) levels.
- Subject has had myocardial infarction within 6 months prior to enrollment , or NYHA(New York Hospital Association) Class III or IV heart failure (see APPENDIX VI), Ejection Fraction $<$ 35%, uncontrolled angina, severe uncontrolled ventricular arrhythmias, electrocardiographic evidence of acute ischemia or active conduction system abnormalities.
- Female subject who is pregnant or lactating.
- Subject has known HIV infection
- Subject has known active hepatitis B or hepatitis C infection.
- Subject has active viral or bacterial infections or any coexisting medical problem that would significantly increase the risks of this treatment program.
- Subject is unable to reliably take oral medications
- Subject has known hypersensitivity to dexamethasone, clarithromycin, lenalidomide, or thalidomide
- Subject has a history of thromboembolic event within the past 4 weeks prior to enrollment.
- Subject has any clinically significant medical or psychiatric disease or condition that, in the Investigator's opinion, may interfere with protocol adherence or a subject's ability to give informed consent.
- Subject has previously been treated for multiple myeloma

6.0 PRETREATMENT EVALUATION

6.1 Should be done within four weeks prior to starting treatment, unless otherwise indicated:

- 6.1.1 Complete medical history and physical exam with particular attention to prior transfusions, prior treatment, and radiotherapy. Vital signs, KPS, weight, and height should be recorded
- 6.1.2 Complete Blood Count (CBC) with differential and platelet count.
- 6.1.3 Complete metabolic profile including sodium, potassium, chloride, CO₂, calcium, magnesium, phosphorus, blood urea nitrogen (BUN), serum creatinine and calculated creatinine clearance, glucose, albumin, total protein, alkaline phosphate, total bilirubin, SGOT/AST, SGPT/ALT
- 6.1.4 Lactate dehydrogenase (LDH)
- 6.1.5 Uric Acid
- 6.1.6 TSH
- 6.1.7 Serum protein electrophoresis, serum immunofixation, serum quantitative immunoglobulins, and free serum light chain studies
- 6.1.8 24 hour urine collection for total protein, protein electrophoresis, and immunofixation
- 6.1.9 Beta-2-microglobulin (B2M)
- 6.1.10 C-reactive protein (CRP)
- 6.1.11 Urinalysis including microscopic analysis
- 6.1.12 Serum or urine pregnancy for women in childbearing potential 10 – 14 days and within 24 hours of initiation of treatment

6.2 Within six weeks prior to starting treatment

- 6.2.1 Complete skeletal survey including all long bones, AP pelvis, C-T-L spine, chest, ribs and lateral skull films OR whole body PET/CT scan.
- 6.2.2 Unilateral iliac crest bone marrow aspirate for cytological review, cytogenetics, FISH studies, flow cytometry (when available) and core biopsy for immunohistochemistry.
- 6.2.3 Electrocardiogram

7.0 THERAPUTIC AGENTS

[figure not shown]
7.1 Clarithromycin (Biaxin®)

Clarithromycin, is a semi-synthetic macrolide antibiotic and is active in vitro against a variety of aerobic and anaerobic gram-positive and gram-negative microorganisms. Biaxin® is indicated for the treatment of mild to moderate infections caused by susceptible strains of microorganisms. It is administered as 500 mg tablets (Abbott Laboratories) to be taken orally. It is rapidly absorbed after oral administration and distributes widely into most body tissue with the exception of the central nervous system. Serum concentrations peak within 2 hours, with a T_{max} of 2 to 4 hours. The elimination half-life is about 3 to 4 hours and has primarily renal excretion, however it is also an inhibitor of cytochrome p450 isozyme CYP3A4. There is potential for drug interaction with other substrates of CYP3A4, as listed in **APPENDIX VII**. The administration of other substrates for CYP3A4 should be avoided if possible. If unavoidable, such drugs should be used with caution. Commercial clarithromycin will be used. Subjects will receive a prescription from the investigator for 500 mg tablets for oral administration, which will be obtained from the subject's local pharmacy. Subjects experiencing adverse event may need study treatment modifications.

7.2 Lenalidomide (Revlimid®)

REVLIMID® (lenalidomide), a thalidomide analogue, is an immunomodulatory agent with anti-angiogenic properties. The chemical name is 3-(4-amino-1-oxo 1,3-dihydro -2H-isoindol-2-yl) piperidine-2,6-dione and it has the following chemical structure:

Chemical Structure of Lenalidomide:

3-(4-amino-1-oxo 1,3-dihydro-2H-isoindol-2-yl) piperidine-2,6-dione

The empirical formula for lenalidomide is C₁₃H₁₃N₃O₃, and the gram molecular weight is 259.3.

Lenalidomide is an off-white to pale-yellow solid powder. It is soluble in organic solvent/water mixtures, and buffered aqueous solvents. Lenalidomide is more soluble in organic solvents and low pH solutions. Solubility was significantly lower in less acidic buffers, ranging from about 0.4 to 0.5 mg/ml. Lenalidomide has an asymmetric carbon

atom and can exist as the optically active forms S(-) and R(+), and is produced as a racemic mixture with a net optical rotation of zero.

REVLIMID® (lenalidomide) is available in 5 mg, 10 mg, 15 mg and 25 mg capsules for oral administration. Each capsule contains lenalidomide as the active ingredient and the following inactive ingredients: lactose anhydrous, microcrystalline cellulose, croscarmellose sodium, and magnesium stearate.

7.2.1 Clinical Pharmacology:

The mechanism of action of lenalidomide remains to be fully characterized. Lenalidomide possesses immunomodulatory and antiangiogenic properties. Lenalidomide inhibited the secretion of pro-inflammatory cytokines and increased the secretion of anti-inflammatory cytokines from peripheral blood mononuclear cells. Lenalidomide inhibited cell proliferation with varying effectiveness (IC50s) in some but not all cell lines. Of cell lines tested, lenalidomide was effective in inhibiting growth of Namalwa cells (a human B cell lymphoma cell line with a deletion of one chromosome 5) but was much less effective in inhibiting growth of KG-1 cells (human myeloblastic cell line, also with a deletion of one chromosome 5) and other cell lines without chromosome 5 deletions. Lenalidomide inhibited the expression of cyclooxygenase-2 (COX-2) but not COX-1 in vitro.

7.2.2 Pharmacokinetics and Drug Metabolism:

Lenalidomide, in healthy volunteers, is rapidly absorbed following oral administration with maximum plasma concentrations occurring between 0.625 and 1.5 hours post-dose. Co-administration with food does not alter the extent of absorption (AUC) but does reduce the maximal plasma concentration (Cmax) by 36%. The pharmacokinetic disposition of lenalidomide is linear. Cmax and AUC increase proportionately with increases in dose. Multiple dosing at the recommended dose-regimen does not result in drug accumulation.

Pharmacokinetic sampling in myelodysplastic syndrome (MDS) patients was not performed. In multiple myeloma patients maximum plasma concentrations occurred between 0.5 and 4.0 hours post-dose both on Days 1 and 28. AUC and Cmax values increase proportionally with dose following single and multiple doses. Exposure (AUC) in multiple myeloma patients is 57% higher than in healthy male volunteers.

7.2.3 Pharmacokinetic Parameters:

In vitro (14C)-lenalidomide binding to plasma proteins is approximately 30%.

Metabolism and Excretion:

The metabolic profile of lenalidomide in humans has not been studied. In healthy volunteers, approximately two-thirds of lenalidomide is eliminated unchanged through urinary excretion. The process exceeds the glomerular filtration rate and therefore is partially or entirely active. Half-life of elimination is approximately 3 hours

7.2.4 Drug Supply and Dosage: Subjects will obtain commercially available Revlimid® (lenalidomide) as 5 mg and 25 mg capsules for oral administration through Celgene Corporation's RevAssist® program. All physicians who prescribe lenalidomide for research subjects enrolled into this trial and all research subjects enrolled into this trial must be registered in and must comply with all requirements of Celgene's RevAssist® program.

The planned dose of lenalidomide for investigation is 25 mg/day, orally on days 1-21 followed by a 7-day rest period (28 day cycles). Subjects experiencing adverse events may need study treatment modifications.

If a dose of lenalidomide is missed, it should be taken as soon as possible on the same day. If it is missed for the entire day, it should not be made up.

Patients who take more than the prescribed dose of lenalidomide should be instructed to seek emergency medical care if needed and contact study staff immediately.

7.2.5 Packaging: Lenalidomide will be shipped directly to patients. Bottles will contain a sufficient number of capsules to last for one cycle of dosing.

7.2.6 Storage and Special Handling Instructions: Lenalidomide should be stored at room temperature away from direct sunlight and protected from excessive heat and cold. Females of child bearing potential should not handle or administer the clinical dosage forms unless they are wearing gloves.

7.2.7 Prescribing Information: Lenalidomide will be prescribed in accordance with the RevAssist® program of Celgene Corporation. Per standard RevAssist® requirements all physicians who prescribe lenalidomide for research subjects enrolled into this trial, and all research subjects enrolled into this trial, must be registered in and must comply with all requirements of Celgene's RevAssist® program. Prescriptions must be filled within 14 days unless the patient is a female of childbearing potential, in which case the prescription must be filled within 7 days. **Only enough lenalidomide for one cycle of therapy will be supplied to the patient each cycle.**

7.2.8 Record of Administration: Accurate records will be kept of all study drug administration, including dispensing and dosing, in the source documents.

7.3 Dexamethasone (Decadron®)

Dexamethasone is a synthetic adrenocortical steroid primarily used for its potent anti-inflammatory effects. In addition, it modifies the body's immune response to diverse stimuli. In the treatment of multiple myeloma, dexamethasone has been widely used as a single agent, as well as in combination, for newly diagnosed, relapsed and refractory disease. Pharmacokinetics are characterized by liver metabolism, time to peak serum concentration within 1-2 hours, duration of metabolic effect up to 72 hours and elimination in the urine. Dexamethasone (Decadron®) will be used as 4 mg tablets to be taken orally. Subjects experiencing adverse events may need dosage modification.

8.0 Toxities and Side Effects

Toxicities and adverse events will be scored using CTCAE version 4.0 for toxicity and adverse event reporting. A copy of the CTCAE version 4.0 can be downloaded from the CTEP homepage (<http://ctep.info.nih.gov>). All appropriate treatment areas must have access to a copy of the CTCAE version 4.0.

8.1 Clarithromycin (Biaxin®)

Possible common side effects associated with clarithroymycin are headaches, diarrhea, nausea, abnormal taste, heartburn and abdominal pain. Possible rare side effects are irregular blood counts, shortness of breath, hypoglycemia, anxiety, hallucinations, anxiety, fast heartbeat, and tremors.

8.2 Lenalidomide (Revlimid®)

In clinical trials conducted to date, lenalidomide appears to be well tolerated and has an acceptable safety profile. In Phase I/II trials of lenalidomide, the drug was well tolerated and had a manageable side effect profile. Common side effects of lenalidomide include rash, fatigue, itching, diarrhea, fever, constipation, light-headedness, and leg cramps, which generally are very mild. The most common side effects are mostly related to a drop in platelet or neutrophil counts. Severe side effects which include Stevens-Johnson's syndrome, tumor lysis syndrome, and irregular blood counts are rare. These side effects tend to be the dose limiting toxicities when attempting to achieve a full dose. The teratogenic effects of lenalidomide have not been tested in humans. However because lenalidomide is a derivative of thalidomide, all subjects are instructed to use effective contraception prior to study entry and for the duration of study participation.

Secondary Primary Malignancies

Patients treated with lenalidomide (Revlimid) may be at an increased risk of developing secondary primary malignancies than patients who were not treated with lenalidomide. Preliminary data derived from evaluation of outcomes after longer-term exposure to Lenalidomide (Revlimid) and from controlled clinical trials conducted inside and outside the United States shows an increased incidence of some second primary malignancies, particularly acute myelogenous leukemia (AML), myelodysplastic syndromes, B- cell malignancies, and Hodgkin lymphoma when compared to controls.³⁶

8.3 Dexamethasone (Decadron®)

Possible common side effects of dexamethasone are fluid retention, weight gain, stomach upset or ulcers, and insomnia and mood changes. Possible side effects of dexamethasone that are less common include hyperglycemia, hypertension, muscle weakness, vertigo, headaches, osteoporosis, manifestation of latent diabetes, increased requirements for insulin or oral hypoglycemic agents in diabetics, cataracts, skin changes, necrosis of the hip, and susceptibility to infections.

8.5 Thrombosis Risk

Lenalidomide and thalidomide increase the risk of thrombotic events in patients who are at high risk or with a history a thrombosis, in particular when combined with other drugs known to cause thrombosis. When lenalidomide or thalidomide is combined with other agents such as steroids (e.g. dexamethasone, prednisone), anthracyclines (Doxil, Adriamycin) and erythropoietin the risk of thrombosis is increased. All patients enrolled into this study will take aspirin therapy as outlined in the treatment plan, section 9.1. Concurrent use of recombinant erythropoietin is discouraged due to reports of increased thromboembolic events in patients receiving lenalidomide with erythropoietin.³² Concurrent use of erythropoietin requires full anticoagulation of patients with therapeutic doses of LMWH or coumadin. Anticoagulation should be held for platelet counts <50,000/mm³. Anti-microbial prophylaxis is not required and is left to the discretion of the treating physician.

9.0 Therapeutic Plan

9.1 Treatment

Patients who sign informed consent will be seen in clinic or in the hospital at New York Presbyterian Hospital-Weill Cornell Medical College, by their physician for pretreatment testing as outlined in section 6.0. All prescribers must be registered in the Celgene RevAssist® program in order to prescribe lenalidomide (Revlimid®). Subjects who complete pretreatment evaluations and meet all eligibility criteria may start treatment. All patients will be started on BiRd in 28-day cycles according to the following schedule:

For all subjects, **Dexamethasone** (Decadron®) will be given orally at a dose of 40 mg on days 1, 8, 15, and 22 for each subsequent cycle

For subjects on the BiRd arm only, **Clarithromycin** (Biaxin®) will be given orally at a dose of 500 mg twice a day, beginning on day 1 of cycle 1.

For all subjects, **Lenalidomide** (Revlimid®) will be given orally at a dose of 25 mg/day beginning on day 3 and ending on day 21 of cycle 1, and on days 1-21 of each subsequent cycle.

Due to the risk of thrombosis (see Section 8.5), all patients will begin thromboembolic prophylaxis with aspirin 81mg daily throughout treatment, starting on cycle 1 day 1. Aspirin-intolerant patients, or patients with a prior history of venous thrombosis, should receive prophylactic doses of daily low molecular weight heparin (LMWH). For patients who are unable to take aspirin or LMWH, other antithrombotic agents may be used at the investigators discretion. If warfarin is used, the INR should be monitored frequently to maintain within the goal range of 2-3. Concurrent use of recombinant erythropoietin to treat anemia is discouraged due to reports of increased thromboembolic events in patients receiving lenalidomide with erythropoietin. Concurrent use of erythropoietin requires full anticoagulation of patients with

therapeutic doses of LMWH or coumadin. Anticoagulation should be held for platelet counts <50,000/mm³.

Monitoring for Secondary Primary Malignancies

Due to the potential increased risk of developing secondary primary malignancies associated with lenalidomide treatment, patients will be advised to undergo regular cancer screenings as part of standard of care. Monitoring for development of acute leukemia and Hodgkin's lymphoma will be performed by review of regular blood work, chemistry panel, and LDH at each visit including during follow-up. Particular attention will be paid to the complete blood count differential with a low threshold to investigate emerging cytopenias or altered differential with either bone marrow biopsy or PET scanning if clinically indicated. In addition, men and women will be advised to have a yearly skin exam by a dermatologist and regular colonoscopy screening (every 5 years or earlier, depending on GI recommendations). Women will also be advised to have yearly mammograms and regular cervical cancer screening. Men will also be advised to undergo yearly Prostate-Specific Antigen (PSA) testing.

For information on the risk of venous thromboembolism with combined oral contraception see **Appendix III: Risks of Fetal Exposure, Pregnancy Testing Guidelines and Acceptable Birth Control Methods.**

Cycles will be repeated every 28 days. Patient will return to clinic every 28 days for evaluation of toxicity and response and will remain on study until progression of disease, toxicities become excessive, or until discontinuation for another reason (see Section 9.2). Doses may be modified due to side effects.

Patients who achieve a resolution of monoclonal gammopathy as detected on serum immunofixation or achieve a plateau of disease (no change in quantitative M-spike or free light chains) for > 2 cycles will be transitioned to maintenance therapy. Maintenance therapy will consist of dexamethasone at a dose of 20mg weekly (given on days 1, 8, 15, and 22 of a 28 day cycle) and lenalidomide at a dose of 25 mg/day on days 1-21 of a 28 day cycle (a dose of 15mg/day days 1-21 of a 28 day cycle will be given to patients with a creatinine clearance of < 60 cc/min).

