1.3 Schedule of Assessments

Procedure	Screening <28 days prior to start date (unless otherwise indicated)	Cycle 1 Day 1	Cycle 1 Days 8, 15, 22	All Other Cycles Day 1	End of Study ⁹	Follow- Up Phase (Every 6 months)
Complete medical history with quality of life assessment.	X	X		X		
Physical exam, KPS, vital signs, height and weight	X	X		X		
CBC with differential	X	X	X	X	X	
Complete metabolic profile ^{1,2}	X	X	X	X ²	X	
Generate / review new drug diary		X		X		
Collect / review prior drug diary				X	X	
SPEP, IF, quantitative immunoglobulins ³	X	X		X	X	
Serum free light chains ³	X	X		X	X	
24-hour urine for UTP, UPEP, UIF ³	X	X		X	X	
β ₂ M ³	X					
CRP	X					
Urinalysis	X					
Pregnancy test ⁴	X	X		X	X	
Register patient into RevAssist [®] program ⁵	X					
Skeletal survey, MRI, or whole body PET/CT scan	X ⁶			X ⁸	X ⁸	
Bone marrow biopsy and aspirate ⁷	X ⁶			X ⁸	X ⁸	
Concurrent medication use survey	X	X		X		
Electrocardiogram	X					
Drug dispensation ⁶				Continuous		
Adverse event				Continuous		

monitoring						
Obtain Follow-Up anti-cancer treatments						X
Obtain disease status, physical status, survival information, and if any occurrence of secondary primary malignancies						X

1. Includes sodium, potassium, chloride, CO₂, calcium, blood urea nitrogen (BUN), serum creatinine and calculated creatinine clearance, glucose, albumin, total protein, alkaline phosphatase, total bilirubin, SGOT/AST, SGPT/ALT, LDH, Uric Acid. Phosphorus and magnesium are performed at screening and Cycle 1 Day 1.
2. To include Thyroid Stimulating Hormone (TSH) at screening, and every 3 months beginning with cycle 4 (more often if clinically indicated).
3. UTP = urine total protein; UPEP = urine protein electrophoresis; UIF = urine immunofixation; SPEP = serum protein electrophoresis; IF = serum immunofixation; β₂M = beta-2 microglobulin.

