4.0 INVESTIGATIONAL PLAN

4.1 Study Design

This phase III study, open-label, randomized study investigating lenalidomide and dexamethasone with and without bixin in subjects with newly diagnosed, previously untreated multiple myeloma. Eligible subjects will be randomized in a 1:1 ratio to receive a regimen consisting of either bixin, lenalidomide, and low dose dexamethasone (BiRd arm), or lenalidomide and low dose dexamethasone (Rd arm). Up to 306 patients will be enrolled.

BiRd Arm

Subjects on the BiRd arm will receive bixin, revlimid, and dexamethasone in 28-day cycles. Dosing is as follows:

- Clarithromycin 500mg PO twice daily on days 1-28 for a 28-day cycle. If a dose of clarithromycin is missed, it should be taken as soon as possible on the same day. If it is missed for the entire day, it should not be made up. Vomited doses will not be made up.
- Lenalidomide 25mg PO daily on days 1-21 of a 28-day cycle for patients with a calculated creatinine clearance of ≥ 60 cc/min. Patients with a calculated creatinine clearance of < 60 cc/min will receive 15 mgs PO daily on days 1-21 of a 28 cycle. If a dose of lenalidomide is missed, it should be taken as soon as possible on the same day. If it is missed for the entire day, it should not be made up. Vomited doses will not be made up.
- Dexamethasone 40mg PO will be given on days 1, 8, 15, 22 of a 28-day cycle. Missed or vomited doses will not be made up. If subject cannot tolerate oral dexamethasone, it will be given intravenously.

Rd Arm

Subjects on the Rd arm will receive revlimid, and dexamethasone in 28-day cycles. Dosing is as follows:

- Lenalidomide 25mg PO daily on days 1-21 of a 28-day cycle for patients with a calculated creatinine clearance of ≥ 60 cc/min. Patients with a calculated clearance of < 60 cc/min will receive 15 mgs PO daily on days 1-21 of a 28 cycle. If a dose of lenalidomide is missed, it should be taken as soon as possible on the same day. If it

is missed for the entire day, it should not be made up. Vomited doses will not be made up.

- Dexamethasone 40mg PO will be given on days 1, 8, 15, 22 of a 28-day cycle. Missed or vomited doses will not be made up. If subject cannot tolerate oral dexamethasone, it will be given intravenously.

Correlative studies: Relative dose intensity: Projected total dose per cycle of each component of assigned drug will be divided by the actual dose received and a ratio will be assessed for each cycle delivered.

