9.6 Dose Modification

Doses of study medications will be modified for toxicity as listed below in Tables 1, 2a, and 2b. Doses must be adjusted for adverse events deemed related to study drug by the investigator. Doses may be adjusted for adverse events related to study medications not listed below at the discretion of the investigator.

Unless otherwise noted, other drugs in the regimen should be continued when the dosing of one or more drugs is delayed due to toxicity.

During BiRd therapy, if toxicity occurs that would indicate an interruption in treatment, the toxicity should be attributed to one or more drugs in the BiRD regimen and dose modifications instituted as instructed in the “Action” column of the table below based on attribution. During maintenance therapy, if toxicity occurs that would indicate a lenalidomide dose modification, toxicity should be attributed to lenalidomide and dose modifications instituted as instructed in the “Action” column of the table below based on attribution.

Table 1: Dose Reduction Steps:

Lenalidomide Dose Reduction

Starting Dose	Lenalidomide PO 25mg/day on days 1-21 of a 28 day cycle
Dose Level -1	Lenalidomide PO 15mg/day on days 1-21 of a 28 day cycle
Dose Level -2	Lenalidomide PO 10 mg/day on days 1-21 of a 28 day cycle
Dose Level -3	Lenalidomide PO 5 mg/day on days 1-21 of a 28 day cycle
Dose Level -4	Lenalidomide PO 5 mg every other day for on days 1-21 of a 28 day cycle

Dexamethasone Dose Reduction

Starting Dose	40 mg PO on days 1, 8, 15 and 22 of a 28 day cycle
Dose Level -1	20 mg PO on days 1, 8, 15 and 22 of a 28 day cycle
Dose Level -2	8 mg PO on days 1, 8, 15 and 22 of a 28 day cycle
Dose Level -3	8 mg PO on days 1 and 15 of a 28 day cycle
Dose Level -4	4 mg PO on days 1 and 15 of a 28 day cycle

Clarithromycin Dose Reduction

Starting Dose	500 mg BID PO days 1-28 of a 28 day cycle
Dose Level -1	250 mg BID PO days 1-28 of a 28 day cycle

Dose Level -2	250 mg PO daily on days 1-28 of a 28 day cycle
Dose Level -3	250 mg PO daily on days odd days of a 28 day cycle
Dose Level -4	Discontinue drug

Table 2a: RD Dose Modification Instructions

Toxicity	NCI Toxicity Grade	Action

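### Section 9.1 orders induction lenalidomide at 25 mg/day with no renal exception, while 4.1 requires 15 mg/day in both arms when creatinine clearance is below 60 cc/min

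*Combined protocol and SAP*

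**What the plan says.** **Section 4.1** sets the lenalidomide dose by calculated creatinine clearance, once for each arm. At 60 cc/min or more the dose is 25 mg on days 1 to 21. Below 60 it is lower. For BiRd: "Patients with a calculated creatinine clearance of < 60 cc/min will receive 15 mgs PO daily on days 1-21 of a 28 cycle". For Rd: "Patients with a calculated clearance of < 60 cc/min will receive 15 mgs PO daily on days 1-21 of a 28 cycle".

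**Section 9.1** (induction), addressing all subjects, says lenalidomide "will be given orally at a dose of 25 mg/day beginning on day 3 and ending on day 21 of cycle 1", then on days 1 to 21 of each later cycle. Renal function is not mentioned.

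**Section 9.1** (maintenance) does carry the exception: "a dose of 15mg/day days 1-21 of a 28 day cycle will be given to patients with a creatinine clearance of < 60 cc/min".

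Three other places give 25 mg without the renal rule:
- Section 7.2.4: "The planned dose of lenalidomide for investigation is 25 mg/day, orally on days 1-21".
- Section 9.6, Table 1, lenalidomide starting dose: "Lenalidomide PO 25mg/day on days 1-21 of a 28 day cycle".
- Both example drug diaries in Appendix VIII.

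Section 5.1 requires creatinine clearance of at least 45 cc/min. Footnote 1 to the Schedule of Assessments (1.3) includes "serum creatinine and calculated creatinine clearance" in the metabolic profile, so the information needed to apply the 4.1 rule is collected.

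**The concern.** Sections 4.1 and 9.1 both order induction dosing. They give different starting doses for the same eligible patients, and the documents contain no rule of precedence. Because 9.1 states the renal exception for maintenance, someone prescribing from 9.1 could reasonably infer that the reduction begins only there. Read literally, a patient with stable clearance of 50 cc/min would get 25 mg in induction and 15 mg in maintenance. Nothing in the protocol explains such a pattern.

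What is at stake is safety in an identifiable subgroup. Section 7.2.3 reports that in healthy volunteers "approximately two-thirds of lenalidomide is eliminated unchanged through urinary excretion". Section 3.7 reports that the phase I studies found myelosuppression dose-limiting and a maximum tolerated dose of 25 mg/day. A patient at 45 to 59 cc/min dosed from 9.1 would therefore start at that maximum, although 4.1 calls for 15 mg, and would stay there until toxicity forced a reduction or maintenance began.

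**Working it through.** The plan states no figure of its own here, so the check compares the two instructions for a patient with clearance of 45 to 59 cc/min.

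**Inputs**
- 9.1 induction: 25 mg/day, days 3 to 21 in cycle 1 (19 days), days 1 to 21 in later cycles (21 days).
- 4.1, clearance below 60, either arm: 15 mg/day, days 1 to 21 (21 days) in every cycle.
- 5.1: lower limit for entry 45 cc/min.

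**Daily dose:** 25 / 15 = 1.67, or +67%.

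**Dose per cycle** = daily dose × dosing days:

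| | 9.1 | 4.1 | Difference | Ratio |
|---|---|---|---|---|
| Cycle 1 | 19 × 25 = 475 mg | 21 × 15 = 315 mg | +160 mg | 1.51 |
| Each later induction cycle | 21 × 25 = 525 mg | 21 × 15 = 315 mg | +210 mg | 1.67 |

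**Cumulative dose.** Induction length is not fixed; it ends on response or plateau. The range below assumes no holds, no reductions and no move to maintenance within the cycles shown:

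| Induction cycles | 9.1 | 4.1 | Difference | Ratio |
|---|---|---|---|---|
| 3 | 475 + 2 × 525 = 1525 mg | 3 × 315 = 945 mg | +580 mg | 1.61 |
| 6 | 475 + 5 × 525 = 3100 mg | 6 × 315 = 1890 mg | +1210 mg | 1.64 |
| 12 | 475 + 11 × 525 = 6250 mg | 12 × 315 = 3780 mg | +2470 mg | 1.65 |

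The cumulative ratio stays a little under 1.67 only because 9.1 starts two days later in cycle 1.

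**Start day.** This is a separate, smaller inconsistency. Section 9.1 starts cycle 1 lenalidomide on day 3; both medication schedules numbered 1.1, section 4.1 and section 7.2.4 start it on day 1. For a patient correctly on 25 mg this gives 475 against 525 mg in cycle 1 only: 475 / 525 = 0.905, or 9.5% less.

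**The case against.** The strongest reply is that the correct dose is already in the protocol. Section 4.1 is itself a dosing section, sets out each arm in full, and states the 15 mg rule twice. A specific renal rule would usually be read as qualifying a general dose. The reference in 9.1 to all subjects most naturally means both arms, since the clarithromycin line beside it is restricted to BiRd. The same section also says every patient starts on BiRd, which cannot be literal in this randomised comparison, so 9.1 has to be read alongside 4.1 in any case. The other places are weaker evidence: 7.2.4 is a drug description, Table 1 is a toxicity step-down ladder, and the diaries are only examples. Weekly blood counts in cycle 1 and the hold-and-reduce rules limit harm.

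Much of this is fair. A careful site working from 4.1 would dose correctly, and the cumulative totals above restate a single ratio under an unfavourable assumption. But reading all subjects as both arms still leaves the 25 mg unqualified. The maintenance exception in 9.1 makes its absence for induction look deliberate. The hold-and-reduce rules act only after toxicity has appeared, whereas the renal rule is preventive. The omission and the arithmetic are not in dispute.

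**Conclusion.** The concern holds. For patients at 45 to 59 cc/min, the induction text of 9.1 contradicts 4.1 by 25 against 15 mg/day (+67%). That is 160 mg more in cycle 1 and 210 mg more in each later induction cycle.

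The figure applies only where a site follows 9.1 rather than 4.1. It is a ratio of ordered doses. The documents give no exposure or toxicity data at this level of clearance and do not say how many such patients are expected, so neither the harm nor its frequency can be estimated. The conflict is the same in both arms, and no bias in PFS or EFS is claimed.

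It is still a must-fix. The text as written orders a starting dose that the protocol's own renal rule forbids for a group it admits. The day 3 against day 1 discrepancy is real but minor.

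**What to change.** - **Section 9.1, induction:** insert the 4.1 rule, 25 mg/day for clearance of 60 cc/min or more and 15 mg/day below 60, for both arms.
- **Section 7.2.4 and Table 1 of 9.6:** cross-reference that rule. State in Table 1 that a patient who starts at 15 mg steps next to 10 mg. The ladder implies this, since 15 mg is level -1, but saying so prevents a one-level reduction being read as no change.
- **Appendix VIII:** leave the lenalidomide dose blank in both diaries, to be completed for each patient.
- **Cycle 1 start day:** use one day throughout. Day 1 matches 1.1, 4.1 and 7.2.4; if day 3 is intended, change those sections instead.
- **Relative dose intensity (4.1):** confirm that the projected dose is the one assigned under the renal rule, which is the natural reading.

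The cost is a protocol wording amendment and revised diary templates. Sample size, endpoints and analysis do not change.
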